12-lead ECG	Х					X	Either Fridericia or Bazett method of correction is acceptable for QT.
Efficacy assessments						•	·
Tumor imaging/response assessments	X			X*			* After efficacy analysis is complete, imaging to be performed per standard of care. Complete response or PR should be confirmed by imaging at least 4 weeks after initial documentation.
ECOG performance status	Х	Х	Х		Х		
Post study anticancer therapy status					X	X	
Survival status					Х	Х	

Table 3:Schedule of Activities (Continued)

	Screening		Treat	ment		Follow-Up	
Visit Day (Range)	28 Days	Cycle 1 Day 1	Cycle ≥ 2 Day 1 (± 3 d)	Q8W (± 7 d)	EOT ^a	28 Days After Last Dose (± 7 d)	Notes
Clinical laboratory assessments							
Serum chemistries	X	X*	Х			Х	* Not necessary on C1D1 if performed during screening within 7 days on C1D1.
Hematology	X	X*	Х			Х	* Not necessary on C1D1 if performed during screening within 7 days on C1D1.
Lipid panel (fasting)	X						
Coagulation panel	X						
Thyroid panel	X		X*			Х	* Every third cycle (C4, C7, C10, etc).
Urinalysis	X						
Pregnancy testing	X	X*	X		X**	X**	 * Not necessary on C1D1 if performed during screening within 7 days on C1D1. ** Can be performed at either EOT visit or 28 days after last dose. Timing and type of testing may be adjusted based on country-specific requirements.

a If EOT is ≥ 21 days postdose, the EOT visit will also serve as the 28-day follow-up visit. If EOT is < 21 days postdose, the 28-day follow-up visit is required.

Table 4	4: Ph	armacokinetic			Sample	Collect	tions				
			Cycle 1	Cycle 2 Day 1	Tre Cycle 4 Day 1	eatment P Cycle 6 Day 1	eriod Cycle 7 Day 1	Cycle 8 Day 1	Cycle 12 Day 1		
Sample	Collection	Purpose/Analysis	Day 1	$(\pm 3 d)$	$(\pm 3 d)$	$(\pm 3 d)$	$(\pm 3 d)$	$(\pm 3 d)$	$(\pm 3 d)$	ЕОТ	Notes
Serum	PK serum	РК	X*	X	X	X				Xª *	Samples will be collected preinfusion and 10 minutes postinfusion (± 10 minutes) on Day 1 of Cycles 1, 2, 4 and 6. * Additional PK samples will be collected 4 hours (± 15 minutes) postinfusion on Day 1 of Cycle 1 and at EOT.

^a A sample will be collected at the EOT visit or, if no separate EOT visit is performed, at the 28-day safety follow-up visit.

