4. STUDY DESIGN

4.1. Overall Design

This study is a Phase 2, open-label, multicenter study designed to assess the clinical activity and safety of INCMGA00012 in participants with advanced solid tumors where the efficacy of PD-1 inhibitors has previously been established. Participants with the following tumor types will be enrolled into disease-specific cohorts:

- Treatment-naive metastatic NSCLC with high PD-L1 expression (TPS \geq 50%) and no EGFR, ALK, or ROS activating genomic tumor aberrations.
- Locally-advanced or metastatic urothelial cancer in cisplatin ineligible patients (determined by the investigator) whose tumors express PD-L1 (CPS \geq 10) of PD-L1).
- Unresectable or metastatic melanoma.
- Locally advanced or metastatic clear-cell RCC without prior systemic treatment.

The primary endpoint is ORR as determined by RECIST v1.1 as determined by the investigator.

The study consists of 3 periods: screening, study drug treatment, and follow-up.

All eligible participants will receive INCMGA00012 at the RP2D of 500 mg IV Q4W. Treatment will be administered by IV infusion over 30 minutes on Day 1 of each 28-day cycle. Subsequent treatment cycles may be delayed due to toxicity for up to 12 weeks (see Section 6.5 and Table 10).

Participants unable to restart study drug treatment ≤ 12 weeks from the start of the treatment delay due to toxicity will be permanently discontinued from study treatment.

Treatment breaks of greater than 12 weeks for reasons other than toxicity (eg, for targeted radiotherapy or surgical resection of oligometastatic disease) will be considered on a case-by-case basis by the medical monitor. Treatment with study drug may continue up to 2 years in the absence of disease progression (see Section 8.2), intolerable toxicity, death, withdrawal of consent, lost to follow-up, or premature discontinuation for any other reason. Participants who have been treated for at least 6 months and achieve a confirmed CR may discontinue INCMGA00012 after 2 additional cycles upon consultation with the medical monitor. Patient management should follow either RECIST v1.1 (see Section 8.2.1) or iRECIST (see Section 8.2.2), with the decision to treat beyond conventional RECIST progression documented in the study file.

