A participant may receive up to 2 years of study drug in the absence of disease progression or unacceptable toxicity. Participants will be evaluated for AEs/SAEs for approximately 28 days after the last dose of study drug and will be followed for irAEs for approximately 90 days after the last dose of study drug or until the start of a new anticancer therapy, whichever occurs first. The 90-day visit may be conducted via phone call. Survival follow-up is not required of participants who have discontinued study drug once the primary efficacy analysis is completed. The primary efficacy analysis will be performed once all participants have been followed for at least 6 months from the start of treatment or have prematurely discontinued study treatment. Thereafter, participants will be treated with INCMGA00012 if they derive clinical benefit as per standard of care for the disease and local guidelines.

CONFIDENTIAL

The complete study-specific assessment schedule required for participants in this clinical study is presented in Table 3. The analytes to be evaluated in the safety laboratory analyses are found in Table 12. Details regarding the sample collection for PK analyses are defined in Table 4.

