8.3.1. Adverse Events

Adverse events will be monitored from the time the participant signs the ICF until at least 28 days after the last dose of study drug. Immune-related AEs will be collected until 90 days after the last dose of study drug. The 90-day visit may be conducted via phone call. Adverse events that begin or worsen after informed consent should be recorded on the Adverse Events Form in the eCRF regardless of the assumption of a causal relationship with the study drug. Conditions that were already present at the time of informed consent should be recorded on the Medical History Form in the eCRF. Adverse events (including laboratory abnormalities that constitute AEs) should be described using a diagnosis whenever possible rather than by individual underlying signs and symptoms. Adverse events judged to be potentially immune-related should be described on the appropriate eCRF (recommended diagnostic algorithms are provided in the Study Procedures Manual).

Adverse events will be reported by the participant (or, when appropriate, by a caregiver, surrogate, or the participant's legally authorized representative). The investigator and any qualified designees are responsible for detecting, documenting, and recording events that meet the definition of an AE or SAE and remain responsible for following-up on AEs that are serious, considered related to the study drug/procedures, or that caused the participant to discontinue the study drug. Care will be taken not to introduce bias when detecting AEs and/or SAEs. Open-ended and nonleading verbal questioning of the participant, such as "How are you feeling?" is the preferred method to inquire about AE occurrences. Adverse events may also be

detected when they are volunteered by the participant during the screening process or between visits, or through physical examinations, laboratory tests, or other assessments. The definition, reporting, and recording requirements for AEs are described in Section 9.

All SAEs will be recorded and reported to the sponsor or designee within 24 hours. The investigator will submit any updated SAE data to the sponsor within 24 hours of it being available.

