8.7. End of Treatment and/or Early Termination

Once a participant permanently discontinues study treatment, the EOT visit should be conducted, and the data should be entered in the EOT visit in the eCRF. If the EOT visit coincides with a regular study visit, the EOT evaluations will supersede those of that scheduled visit. Should study treatment discontinuation occur < 21 days after the final dose of study treatment, a 28-day safety follow-up visit is required and should be conducted according to Table 3. If the EOT visit occurs ≥ 21 days after the last study treatment, only a single EOT/28-day safety follow up is required; otherwise, the EOT visit will also serve as the 28-day safety follow-up visit, and the EOT assessment schedule will be followed.

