Follow-Up of Adverse Events and Serious Adverse Events

- The investigator is obligated to perform or arrange for the conduct of supplemental measurements and/or evaluations as medically indicated or as requested by the sponsor to elucidate the nature and/or causality of the AE or SAE as fully as possible. This may include additional laboratory tests or investigations, histopathological examinations, or consultation with other health care professionals.
- New or updated information will be recorded in the originally completed eCRF.
- Any updated SAE data will be submitted to the sponsor (or designee) within 24 hours of receipt of the information.
- Once an AE is detected, it should be followed until it has resolved or until it is judged to be permanent; assessment should be made at each visit (or more frequently if necessary) of any changes in severity, the suspected relationship to the study drug, the interventions required to treat the event, and the outcome.
- When the severity of an AE changes over time for a reporting period (eg, between visits), each change in severity will be reported as a separate AE until the event resolves.

9.4. **Reporting of Serious Adverse Events**

Regardless of suspected causality (eg, relationship to study drug or study procedures), all SAEs occurring after the participant has signed the ICF through 28 days after the last dose of study drug must be reported to the sponsor (or designee) within **24 hours** of learning of its occurrence, unless otherwise specified by the Protocol. Serious AEs that are irAEs must be reported until 90 days after the last dose of study drug or the start of a new anticancer therapy, whichever occurs first. The investigator will submit any updated SAE data to the sponsor (or designee) within 24 hours of it being available.

Investigators are not obligated to actively seek AE or SAE information after conclusion of the study participation. However, if the investigator learns of any SAE, including a death, at any time after a participant has been discharged from the study, and he/she considers the event to be reasonably related to the study drug or study participation, the investigator must notify the sponsor (or designee) within 24 hours of becoming aware of the event.

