4.1.7. On-Treatment Assessment/Event

Safety summaries and selected summaries of deaths will summarize only on-treatment assessments/events. On-treatment assessment/event is defined as any assessment/event obtained in the time interval:

 Date of first infusion of INCMGA00012 through date of last infusion of INCMGA00012 + 90 days;

Adverse events that begin or worsen after informed consent obtained should be recorded in the Adverse Events CRF.

If the last date of study drug administration is missing, on-treatment assessments/events include any assessment/event recorded in the database and those that occur after the start date of study drug unless there are other datasets indicating treatment is ended.

Data listings will include all assessments/events, flagging those that are not on-treatment assessments/events.

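### The single last-infusion + 90-day safety window in SAP 4.1.7 does not match the protocol's adverse event collection periods and can close before a late safety visit

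*SAP*

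**What the plan says.** **Analysis window.** SAP 4.1.7 restricts safety summaries, and selected death summaries, to on-treatment data, defined as "Date of first infusion of INCMGA00012 through date of last infusion of INCMGA00012 + 90 days". Event types are not separated, and new anticancer therapy does not end the window. Data outside it are kept in listings only: "Data listings will include all assessments/events, flagging those that are not on-treatment assessments/events". The TEAE definition in SAP 8.2.1 has no end date, so 4.1.7 supplies the only cap.

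**Collection.** Protocol 4.1: "Participants will be evaluated for AEs/SAEs for approximately 28 days after the last dose of study drug and will be followed for irAEs" for about 90 days or until new anticancer therapy, whichever comes first. Protocol 9.4 requires reporting of "all SAEs occurring after the participant has signed the ICF through 28 days after the last dose of study drug" and gives serious irAEs the same 90-day or new-therapy limit. Table 3 and section 8.8.1 agree on irAEs. Section 8.3.1 is worded differently: AEs are monitored "until at least 28 days after the last dose of study drug. Immune-related AEs will be collected until 90 days after the last dose", with no stop at new therapy.

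**Timing of the last visit.** A separate safety visit is due 28 ± 7 days after the last dose. If EOT falls 21 days or more after the last dose, "the EOT visit will also serve as the 28-day follow-up visit" (Table 3, footnote a). Section 8.7 likewise says "only a single EOT/28-day safety follow up is required". Neither gives a latest day. On toxicity holds, Protocol 4.1 says that participants who cannot restart within "12 weeks from the start of the treatment delay due to toxicity will be permanently discontinued from study treatment".

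**The concern.** Two separate things go wrong when one fixed window meets these rules.

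First, between about day 29 and day 90 the sites are asked to look for irAEs but not, as a rule, for other AEs. Non-immune events in that period reach the database by partial routes, such as a late SAE judged related to study drug (Protocol 9.4) or a change in severity of an AE already being followed (Protocol 9.3). A single TEAE percentage then combines two levels of ascertainment, and a reader of the table cannot tell them apart. Because SAP 8.2.2 identifies irAEs by preferred term whatever the investigator's view of causality, events starting after a new anticancer therapy can also enter the irAE tables.

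Second, the window counts from the last infusion while the last safety visit can move with a dose hold. The participants concerned are those who stop after unresolved toxicity, where the final safety data are of most interest. The follow-up visit is also the only postbaseline visit at which Table 3 schedules an ECG.

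Safety is a secondary objective, so the tables should state clearly what period they cover.

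**Working it through.** The 90 days is a definition, so there is no planned figure to reproduce. The check is a day count with the last infusion as day 0.

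**Inputs**
- Window end: day 90 (SAP 4.1.7).
- AE/SAE collection: about 28 days (Protocol 4.1, 9.4); at least 28 days (8.3.1).
- Separate safety visit: day 28 ± 7 (Protocol 8.8.1, Table 3).
- Cycle: 28 days (SAP 4.1.6), with a ± 3-day dosing window (Table 3).
- Toxicity hold: up to 12 weeks = 84 days from the start of the delay (Protocol 4.1).
- EOT doubles as the safety visit from day 21, with no upper limit (Table 3 footnote a; 8.7).

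**1. Window longer than collection (non-immune AEs)**
- From day 28: 90 − 28 = 62 days.
- From the latest scheduled visit, day 28 + 7 = 35: 90 − 35 = 55 days.
- For irAEs the 90 days agree; only the stop at new therapy is missing.

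These are calendar days. The documents give no late-event rates, so they cannot be turned into a change in TEAE percentages.

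**2. Window shorter than the visit schedule**
- Separate safety visit: days 21 to 35, always inside day 90.
- Full 12-week hold from a dose missed on day 28, EOT at the end of the hold: 28 + 84 = day 112, which is 112 − 90 = 22 days outside. With the ± 3-day dosing window: days 109 to 115, or 19 to 25 days outside.
- Shortest hold that takes the visit past day 90: anything over 90 − 28 = 62 days (62/7 = 8.9 weeks).
- If the 12 weeks run from the last dose instead: day 84, which is 6 days inside.

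The last case is not hypothetical. For Grade 3 or 4 hypophysitis, Table 10 counts 12 weeks for resolution from the last dose, whereas Protocol 4.1 counts from the start of the delay. The protocol should reconcile the two starting points; which one applies is not a matter for this point. Breaks for reasons other than toxicity may exceed 12 weeks with approval (Protocol 4.1), and no maximum is stated.

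**3. What is lost at a visit after day 90**
- Left out of summaries: that visit's laboratory tests, vital signs and scheduled follow-up ECG, and any AE starting after day 90.
- Kept: any AE that started by day 90, even if first reported at the late visit, because the event itself lies inside the interval.
- Everything stays in the flagged listings.

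**4. Which texts apply**

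SAP 2.1 bases the SAP on Protocol Amendment 3 but keeps it in force for later amendments. The amendment log places the 28/90-day clarification in Amendment 4 (25 NOV 2020), after SAP Amendment 1 (23 JUN 2020). That probably explains the mismatch, but the finding rests on the current protocol and SAP texts.

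**The case against.** The strongest reply is that a long window is the cautious choice. It matches the irAE period, drops no AE that the protocol requires, and suits a SAP that treats every AE as treatment-emergent unless clearly shown otherwise. Section 8.3.1 makes 28 days a floor. The study has no comparator and no hypothesis test, so no between-arm contrast can be biased. With a half-life of about 17 days (Protocol 2.1.1), day 90 is about 90/17 = 5.3 half-lives after the last dose. All of this stands, and it is why the 90-day tables should remain.

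A reader might infer that non-immune AEs after day 28 should be removed from the tables. The documents do not support that. Protocol 9.3 requires an AE to be followed to resolution or permanence and each change in severity to be reported as a separate AE. A cut by record date would remove, for example, a Grade 4 worsening on day 45 of an AE that began on day 20 from the Grade 3 or higher table, or a fatal one from the fatal table.

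A reader might also infer that everything reported at a late visit is lost. It is not: AEs that began by day 90 still count. The late visit also needs a long hold that ends in discontinuation, and the decision to stop may come earlier than week 12. How often this happens cannot be told from the documents.

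Finally, one might want a different window for each participant according to the protocol version in force. The earlier versions are not supplied, so that rule cannot be built from these documents.

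**Conclusion.** The point holds in two limited parts and is worth considering rather than essential.

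- **Mixed ascertainment.** For 62 days after day 28 (55 after a day-35 visit), the all-TEAE summaries include non-immune events that were not systematically collected. The direction is extra, incompletely captured events, not missing required ones. The effect on counts is unknown.
- **Early closure.** A hold of more than 62 days from a missed dose, followed by discontinuation, places the combined visit outside the window, by about 22 days after a full 12 weeks. This assumes that the hold is counted from the missed dose, that EOT takes place when the hold ends, and that the follow-up assessments in Table 3 are done at the combined visit. Counted from the last dose, the visit falls at about day 84 and nothing is lost.

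Both parts assume that 4.1.7 governs the TEAE tables, since 8.2.1 does not restate a cap. The harm is modest: the tables are descriptive, irAEs have their own tables, and listings keep all data. ORR and OS do not depend on this window.

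**What to change.** 1. In SAP 4.1.7, end the window at the later of last infusion + 90 days and the actual EOT/28-day safety visit, for AEs, laboratory tests, vital signs and ECG alike. This works whichever way the 12 weeks are counted.
2. Keep the existing TEAE tables on that window. Add all-TEAE, serious and Grade 3 or higher summaries restricted to AEs starting by the later of last dose + 28 days and the actual safety visit. Assign each AE by the onset date of the original event, so that later worsening recorded as a new AE under Protocol 9.3 stays with it in the severity and fatal tables.
3. In the irAE tables, identify events starting after new anticancer therapy and present results with and without them.
4. Reconcile Protocol 8.3.1 with Table 3, 8.8.1 and 9.4. Also reconcile SAP 6.5, which summarizes concomitant medications to 90 days after the last dose, with Protocol 6.6, which generally records them to 28 days but keeps those given for AEs, and those for SAEs or irAEs whenever given.

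The cost is SAP wording, a few extra tables, and a programming rule to link successive severity records of one AE. No new data are needed. One limit remains: the restricted summaries will still run longer for participants with a late visit, which a footnote should say.

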4.2. Variable Definitions

The following variables will only be calculated if not reported on the eCRF.

4.2.1. Body Mass Index

Body mass index will be calculated as follows:

BMI $(kg/m^2) = [weight (kg)] / [height (m)]^2$.

4.2.2. Creatinine Clearance

Creatinine clearance by Cockcroft-Gault equation (Cockcroft and Gault 1976) is estimated from serum creatinine (mg/dL) determination using the following formula:

Creatinine clearance (mL/min) = $[140 - age (years)] \times weight (kg) \times \{0.85* \text{ for female participants}\}$ / $[72 \times serum \text{ creatinine (mg/dL)}]$. *Note: For male participants use 1.0.

4.2.3. Prior and Concomitant Medication

Prior medication is defined as any nonstudy medication started before the first dose of INCMGA00012.

Concomitant medication is defined as any nonstudy medication that is started accordingly:

- Before the date of first administration of INCMGA00012 and is ongoing throughout the study or ends on/after the date and time of first study drug administration.
- On/after the date of first administration of INCMGA00012 and is ongoing or ends during the course of study drug administration.

A medication could also be classified as "both prior and concomitant medication" if the end date is on or after the date of first administration of INCMGA00012. In the listing, it will be indicated whether a medication is prior-only, concomitant-only, or both prior and concomitant medication.

For the purposes of analysis, all medications will be considered concomitant medications unless the medications can unequivocally be defined as not concomitant (ie, if start date and end date are all missing, then the medication is considered as concomitant medication). See Section 4.1.5 for handling if missing/incomplete data.

5. STATISTICAL METHODOLOGY

5.1. General Methodology

Unless otherwise noted, SAS® software (SAS Institute Inc, Cary, NC; v9.4 or later) will be used for the generation of all tables, figures, and statistical analyses. Descriptive summaries for continuous variables will include, but not be limited to, the number of observations, mean, standard deviation, median, minimum, and maximum. Descriptive summaries for categorical variables will include the number and percentage of participants in each category.

5.2. Treatment Groups

Analysis will be presented by disease-specific cohorts: melanoma, NSCLC, urothelial cancer (bladder cancer), and RCC. Safety data will also be presented for all cohorts combined.

5.3. Analysis Populations

5.3.1. Full Analysis Set

The FAS includes all participants who received at least 1 dose of study drug. The FAS will be used for demographics, disposition, baseline characteristics, and all efficacy analyses.

